### **9.3. Vital Sign Measurements**

Supine (laying face upward) blood pressure, heart rate/pulse, temperature, and respiratory rate will be measured after the patient has been resting for 5 minutes. Vitals signs will be measured prior to any blood draw that occurs at the same time point. Vital signs will be measured according to the time points in the schedules of procedures and visits (Section 14.1).

Summary tabulations (i.e. n, mean, SD, median, minimum and maximum) for the observed values and changes from baseline will be presented for vital sign data for patients in the Safety population. Changes from baselines (APD334-003 baseline and APD334-005 baseline) to each scheduled post-baseline time point and visit will be presented. Baseline for APD334-003 study is defined as last measurement before first dose of study medication in APD334-003 study, and baseline for APD334-005 study is defined as last pre-enrollment measurement (APD334-005 Day 1 pre-dose).

All vital sign data by patient will be presented in a listing.

[figure not shown]
### **9.4. Physical and Neurological Examination**

[figure not shown]
Physical and neurological examinations will be listed.

### **9.5. Safety ECG (12-lead)**

Safety ECGs will be recorded from an ECG machine (12-lead). All safety ECGs will be obtained as single tracings, with the exception of the pre-treatment ECG obtained on Day 1, which is a triplicate recording.

All patients will have a standard 12-lead ECG performed during the study as clinically indicated. Intervals to be provided for each ECG are: RR, PR, QRS, QT, QT interval corrected for heart rate (QTc), QTc corrected by Bazett's (QTcB), and QTc corrected by Fridericia's (QTcF).

### 9.6. Lymphocyte Count

Summary tabulations (i.e. n, mean, SD, median, minimum and maximum) for the absolute lymphocyte counts, absolute changes from baselines [REDACTED], and percentage changes from baselines at each visit [REDACTED] will be presented for patients [REDACTED].

### 9.7. Other Safety Data

Other safety data will be listed and includes:

- PML Checklist
- Ophthalmoscopy with OCT
- PFT
- Pregnancy test details (only females who are not diagnosed as postmenopausal)

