Exploratory:	 The content of this cell is redacted with black bars. It appears to be a list of items, each preceded by a vertical bar, but the text is obscured.
Safety Assessments:	

• Physical & neurological examinations including ophthalmoscopy (and optical coherence tomography [OCT], where available)

• PML checklist

• Clinical laboratory tests to include hematology, serum chemistry, coagulation, and urinalysis

• Vital sign measurements

• Pulmonary Function Tests (PFTs)

• 12-lead electrocardiograms (ECGs)

• Adverse event reporting

	
Data Analyses:	
There is no formal between group inferential comparison for study endpoints. Summary statistics will be provided for primary, secondary, exploratory measures, and additional safety measures. For proportion-based measures, N, frequencies, proportion and its 95% confidence interval (CI) will be produced. For continuous measure, N, mean, median, range, and SD will be produced for observed values, and additional 95% CI for change or percent change from baseline will be produced.
 
Additional analyses may be performed in some subgroups of medical interest, such as sex, age, race, presence or absence of current oral corticosteroid use, previous exposure to TNF<math>\alpha</math> antagonists, baseline fecal calprotectin level, baseline CRP level, and previous treatment received in APD334-003.

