### 6.3 Physical and Neurological Examination

The physical examination, which includes assessments of general appearance, skin, head (eyes, ears, nose, and throat), neck, thyroid, lungs, heart, abdomen, back, lymph nodes, extremities, height and body weight; and the neurological examination, which includes assessments of the neurological system (cranial nerves, motor and sensory function, coordination, and mental status) will be performed by the principal investigator or sub-investigator. The physical and neurological exams performed at the [REDACTED] visit of study APD334-003 will serve as baselines for the APD334-005 study.

The physical examination will also include visual acuity and dilated ophthalmoscopy (by an ophthalmologist) and with OCT (where available) [REDACTED] (to rule out and monitor for any significant retinal disease, including macular edema). Retinal photos will be taken during the baseline visit [REDACTED] and any subsequent unscheduled ophthalmoscopy.

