## 4. GENERAL STATISTICAL CONSIDERATIONS

Continuous data will be summarized using descriptive statistics (i.e., n, mean, median, standard deviation (SD), 90% confidence interval (CI) for change or percent change from baseline, minimum and maximum). For the summary statistics of all numerical variables unless otherwise specified, minimum and maximum will be displayed to the same level of precision as reported. Mean, median and 90% CIs will be displayed to one level of precision greater than the data collected. Standard deviation will be displayed to two levels of precision greater than the data collected.

For proportion-based measures, n, frequencies, proportion and its 90% CI will be produced. The denominator for all percentages will be the number of patients within the treatment group for the analysis set of interest, unless otherwise stated. Percentages will be presented to 1 decimal place. When count data are presented, the percentage will be suppressed when the count is zero in order to draw attention to the non-zero counts. A row denoted “Missing” will be included in count tabulations where specified on the shells to account for dropouts and missing values.

There is no formal between group inferential comparisons for study endpoints due to lack of control group. Summary statistics will be provided for the primary safety endpoint, secondary efficacy endpoints, exploratory efficacy endpoints, and additional safety measures. All analysis summaries will be presented as follows:

Previously Treated in APD334-003 (APD334-005 treatment: 2 mg etrasimod)				APD334-005 treatment:	APD334-005 treatment:
Placebo	1 mg etrasimod	2 mg etrasimod	1 mg & 2 mg etrasimod	2 mg etrasimod	Placebo

[figure not shown]
[figure not shown]
Listings will include a subtitle to indicate both treatments, i.e. treatment received in APD334-003 study and treatment received in APD334-005 study.

[figure not shown]
[figure not shown]
[figure not shown]
If endoscopy was performed prior to Week 46, then last observation carried forward (LOCF) imputation method will be used for the endoscopy subscore. Any endoscopy performed during the APD334-005 extension study (after Week 12 visit) will be used for LOCF imputation.

All data summaries and statistical analyses will be performed using the SAS software version 9.3 or higher (SAS Institute, Cary, NC).

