## 9. SAFETY ANALYSIS

The safety of etrasimod will be monitored throughout the study with safety endpoints being as follows:

- Treatment-emergent adverse events (TEAEs) up to 30 days following discontinuation of the study drug
- Treatment-emergent serious adverse events (SAEs) up to 30 days following discontinuation of the study drug

Additional safety assessments will include:

- Physical & neurological examinations including ophthalmoscopy (and optical coherence tomography [OCT], where available)
- Progressive multifocal leukoencephalopathy (PML) checklist
- Clinical laboratory tests to include hematology, serum chemistry, coagulation, and urinalysis
- Vital sign measurements
- Pulmonary Function Tests (PFTs)
- ECGs
- AE reporting

For analyses based on laboratory measurements, vital signs and ECGs, summary tabulations (n, mean, SD, median, minimum and maximum for actual and change [or percent change] from baseline) will be presented. For analyses based on AEs, frequency and percentage will be presented. The analyses for all safety outcomes (categorical or continuous measures) will use the Safety population.

For analysis based on laboratory measurements, at least 1 laboratory test post-enrollment measurement in the extension study is required for inclusion in the Safety population. When assessing change from baseline, a baseline measurement is also required. Baseline for the safety analysis is defined as the last pre-enrollment measurement (i.e. APD334-005 Day 1 pre-dose). No missing data will be imputed for the safety analysis.

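### Spirometry and ophthalmoscopy/OCT results are listed but not summarised, although SAP Section 4 promises summary statistics for additional safety measures

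*SAP*

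**What the plan says.** SAP Section 4 (General Statistical Considerations) states: "Summary statistics will be provided for the primary safety endpoint, secondary efficacy endpoints, exploratory efficacy endpoints, and additional safety measures". The synopsis of the protocol says much the same under Data Analyses: "Summary statistics will be provided for primary, secondary, exploratory measures, and additional safety measures".

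SAP Section 9 opens a list with "Additional safety assessments will include". Its bullets include pulmonary function tests (PFTs) and, within the physical and neurological examination bullet, ophthalmoscopy with OCT where available. The same section then says which data are tabulated: "For analyses based on laboratory measurements, vital signs and ECGs, summary tabulations" are planned, and adverse events receive frequencies and percentages. PFTs and eye examinations are not named there.

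SAP Section 9.7 settles their output: "Other safety data will be listed and includes" the PML checklist, ophthalmoscopy with OCT, PFTs and pregnancy tests. SAP Section 9.4 also gives only listings for physical and neurological examinations.

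Protocol Section 6.3 states the purpose of the eye examination: "to rule out and monitor for any significant retinal disease, including macular edema". Protocol Section 7.2.2.4 schedules both spirometry and ophthalmoscopy/OCT with retinal photos at Week 46, end of treatment or early termination. Section 7.2.2.3 also schedules spirometry during treatment, at weeks that are blacked out.

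**The concern.** Long-term safety and tolerability is the primary objective, and the study collects spirometry and retinal examinations as safety assessments. Spirometry is numeric and repeated, so the usual way to see a drift is a table of change from baseline. A modest average decline that no investigator reports as an adverse event would appear only as individual rows in a listing. Likewise, a retinal abnormality found on examination but not reported as an adverse event would be counted nowhere.

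The wording adds a practical problem. A programmer following Section 4 would produce summaries of these data; one following Section 9.7 would not. The listing would allow someone to compute a summary later, but it would not have been planned in advance.

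**Working it through.** No arithmetic applies: the documents give no figure on this point, and the question is which output is planned for which measure. The check sets the seven bullets of the additional safety assessments in SAP Section 9 against the output planned for each in the readable text.

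| Item in the SAP Section 9 list | Output planned |
|---|---|
| Laboratory tests | Tables of values and change from both the APD334-003 and APD334-005 baselines, shift tables, listing (9.2) |
| Vital signs | Tables of values and change from both baselines, listing (9.3) |
| ECGs | Named for summary tabulation (9) |
| Adverse events | Number and percentage by system organ class and preferred term, relationship and severity, with separate tables for serious events and discontinuations (9.1) |
| Physical and neurological examinations, including ophthalmoscopy/OCT | Listing (9.4; 9.7 for ophthalmoscopy/OCT) |
| PML checklist | Listing (9.7) |
| PFTs | Listing (9.7) |

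Four of the seven bullets are tabulated and three are only listed. Lymphocyte counts, which have their own Section 9.6, also receive tables.

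1. *Is spirometry different in kind from what is tabulated?* No. The protocol's abbreviations include FEV1, FVC and FEF25-75%, which are continuous. Of the three listing-only bullets, PFTs are the one that yields numeric measurements as its main result. The readable text gives no reason for treating them differently from laboratory values or vital signs.

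2. *Is a summary planned elsewhere?* Not in readable text. Protocol Section 9.8 names adverse events, laboratory parameters, vital signs and ECG. It introduces them as examples of all safety parameters, but it plans no PFT or eye table.

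3. *Is the listing-only choice explained?* SAP Section 12 records other departures from Protocol Amendment 04, such as the move from 95% to 90% confidence intervals. Its readable text does not mention this one.

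4. *What is still counted?* The adverse event definition in protocol Section 6.11.1 covers any unfavourable sign and the worsening of existing conditions. SAP Section 9.1.2 tabulates treatment-emergent events. Macular edema or a respiratory event reported as an adverse event therefore does reach a table.

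Two things are left without a planned table: measured change in spirometry, and ophthalmoscopy/OCT findings not reported as adverse events.

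**The case against.** The strongest reply is that the SAP does not contradict itself. The sentence in Section 4 is general and leaves its term undefined. Section 9 speaks of assessments, not measures, and then names the data to be tabulated; Sections 9.4 and 9.7 assign listings to the rest. Read in that order, a specific rule narrows a general one and every item has a stated output. Read literally, the Section 4 sentence would also require tables for the PML checklist and physical examinations, which few would ask for. This has force: a reader might infer a flat internal contradiction, but the documents support only a mismatch between a general promise and a specific rule.

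A reader might also infer that lung and retinal safety goes wholly unquantified. It does not, because reported events are tabulated. Nor does the SAP drop a table that the protocol specified: the detailed protocol plan has none, and only the synopsis sentence points the other way.

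Other limits stand. The readable text gives a reason for the eye examination but none for spirometry. Neither an APD334-003 baseline for PFT or OCT nor the list of spirometry parameters recorded can be confirmed. SAP Section 10, protocol Section 9.7, parts of SAP Section 12, the schedules and the table shells cannot be read. There is no control group for formal comparison, so a small mean change would be hard to attribute to the drug.

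None of this supplies a summary of the data. The narrowing reading explains how the SAP can be followed; it does not explain why a numeric safety measure should go unsummarised.

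**Conclusion.** The point holds as a reporting gap that is cheap to close. Following Section 9.7 as written, no planned table in the readable text shows average spirometry change or counts examination findings that were not reported as adverse events, although long-term safety is the primary objective. Section 4 and the synopsis would lead a reader to expect both.

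Its size is the number of missing summaries: none planned for PFTs and none for ophthalmoscopy/OCT. A reader might want the precision with which a mean change could be estimated. The documents do not support such a figure, because they state no standard deviation for any spirometry parameter and no sample size. No stated result, endpoint or analysis population changes.

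The conclusion assumes that the parts that cannot be read contain no such table. If the table shells already include them, only the wording of Section 9.7 needs to be brought into line.

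**What to change.** In SAP Section 9.7, keep the listings and add two tables for the Safety population, using the columns of Section 4.

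- **Spirometry.** For each parameter recorded, give observed values and change from the APD334-005 baseline by visit, and change from the APD334-003 baseline where one was collected. Use the Section 9 descriptive statistics (n, mean, SD, median, minimum, maximum).
- **Ophthalmoscopy/OCT.** Give n (%) of patients with a new or worsened post-baseline abnormality among those examined. Show the denominator, separately for OCT, because OCT is done only where available.

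If the sponsor prefers listings only, the alternative is to narrow the Section 4 sentence to the measures that are tabulated and record the decision, with its reason, in Section 12. That removes the mismatch but leaves the data unsummarised.

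The cost is two descriptive tables from data already collected. Without a formal control comparison they would describe change and could not attribute it to treatment; a footnote should say so.

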## 11. INTERIM ANALYSIS

No interim analyses is planned for this study.

## 12. CHANGES IN THE PLANNED ANALYSIS

Under Protocol Amendment 02 (28 Sep 2015) eligible responders on active treatment in the APD334-003 study (who choose to continue on to the APD334-005 study) underwent 1:1 randomization to 2 mg etrasimod q.d. or matching Placebo, while eligible Placebo responders in the APD334-003 study (who choose to continue on to the APD334-005 study) remained on Placebo. Responder patients stayed blinded. Non-responders in the APD334-003 study (who choose to continue on to the APD334-005 study) were administered with open-label 2 mg etrasimod. Under Protocol Amendment 03 (20 Oct 2016) eligible patients (who choose to continue on to the APD334-005 study) must have completed the APD334-003 study and were administered open-label 2 mg etrasimod. Data gathered on patients before Protocol Amendment 03 will follow the Protocol Amendment 03 analyses and data presentation as described in this SAP document. Patients that received 2mg etrasimod under any Protocol Amendment will be pooled into a 2 mg etrasimod group and patients that received placebo prior to Protocol Amendment 03 will be included in a second group. All listings will be presented by these two treatment groups, namely 2 mg etrasimod and Placebo, and by treatment previously received in APD334-003 study.

The following exploratory objectives have been added to the SAP in comparison with Protocol Amendment 04 (27 Mar 2017) to be consistent with the objectives in the APD334-003 study:

[REDACTED]

The following exploratory endpoints have been added to the SAP in comparison with Protocol Amendment 04 (27 Mar 2017) to be consistent with the endpoints in the APD334-003 study:

[REDACTED]

The following exploratory endpoints have been removed from the SAP in comparison with Protocol Amendment 04 (27 Mar 2017), as these are no longer needed:

[REDACTED]

The following subgroup analysis has been added to the SAP in comparison with Protocol Amendment 04 (27 Mar 2017):

[REDACTED]

The following subgroup analyses have been removed from the SAP in comparison with Protocol Amendment 04 (27 Mar 2017), as these have been already evaluated in APD334-003 study and are no longer needed:

[REDACTED]

The 95% CIs have been changed to 90% CIs for all analyses in comparison with Protocol Amendment 04 (27 Mar 2017) to be consistent with the APD334-003 study.

The clinical remission definition has been updated to include “a rectal bleeding score of 0 or 1” in comparison with Protocol Amendment 04 (27 Mar 2017) to be consistent with the definition in final SAP of APD334-003 study.

The clinical response definition has been updated as “a patient has achieved clinical response if he/she meets criteria of clinical remission, or meet criteria of clinical response defined in the protocol.” to be consistent with the definition in final SAP of APD334-003 study.

The following changes have been applied to the Analysis Populations to the SAP in comparison with Protocol Amendment 04 (27 Mar 2017):

- ITT population has been removed – no longer needed as APD334-005 is an open label study
- Definition of CP population has been updated to include “This CP population consists of all patients in the MITT population who completed the extension study” and “Note that CP population will be used only for endpoints that include the endoscopy subscore, unless otherwise stated.” – to be consistent with the definition in final SAP of APD334-003 study
- CP population will be used only for endpoints that include the endoscopy subscore:

[REDACTED]

Sponsor was notified that laboratory tests for five patients [REDACTED] had been sent to local labs for the purpose of safety follow up on blood cell counts after last treatment. Such follow up may still be needed at time of database lock. The local laboratory results will be translated in English and archived in study file. Sponsor will write a section in CSR to describe the findings and to assess the safety issues for these [REDACTED] patients.

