  - Changed study duration from 52 weeks to 46 weeks in total
  - Changed study design to single arm, open-label (2 mg once daily [q.d.]) for APD334-003 responders only and removal of Placebo group
  - Updated secondary [REDACTED] outcome measures to reflect study duration of 46 weeks total (including the APD334-003 study)
  - [REDACTED]
  - Changed Week 52 to Week 46 as End-of-Treatment
  - Removed Primary Safety and Secondary Efficacy hypotheses
  - Removed sample size and power calculations

- Changed 'Randomized' to 'Enrolled' and removed treatment groups
- Removed between group differences and removal of formal statistical analysis
- Amendment 03 (20 Oct 2016) to Amendment 04 (27 Mar 2017)
  - Updated to add proportion of patients who achieve clinical response to secondary endpoints
  - Updated to reflect APD334-003 completers to be eligible for APD334-005 study

More details can be found in Section 12.

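### The single Placebo column in the SAP summary tables combines patients taken off etrasimod with patients who never took it, and should be split by APD334-003 treatment

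*SAP*

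**What the plan says.** SAP section 12 describes how patients reached placebo in the extension. Under Amendment 02, APD334-003 responders who had been taking active drug "underwent 1:1 randomization to 2 mg etrasimod q.d. or matching Placebo". The other source was not randomised: "eligible Placebo responders in the APD334-003 study (who choose to continue on to the APD334-005 study) remained on Placebo". Nobody else was given placebo: "Non-responders in the APD334-003 study (who choose to continue on to the APD334-005 study) were administered with open-label 2 mg etrasimod".

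For analysis, section 12 forms two groups. The first gathers the active-treatment patients of every protocol version: "Patients that received 2mg etrasimod under any Protocol Amendment will be pooled into a 2 mg etrasimod group". The rule for the remaining patients is that "patients that received placebo prior to Protocol Amendment 03 will be included in a second group". It adds that listings will show both groups by the treatment previously received in APD334-003.

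SAP section 4 fixes the table layout: "All analysis summaries will be presented as follows". The columns that follow show 2 mg patients by APD334-003 treatment (placebo, 1 mg, 2 mg, and 1 mg and 2 mg combined), then all 2 mg patients, then one Placebo column. The same section says that no formal between-group comparison will be made.

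Entry rules also changed over time. SAP section 1 says of Amendment 03, "Changed study design to single arm, open-label (2 mg once daily [q.d.]) for APD334-003 responders only and removal of Placebo group", and of Amendment 04, "Updated to reflect APD334-003 completers to be eligible for APD334-005 study".

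**The concern.** A descriptive column is useful only if it describes an identifiable group. Stopping an active drug after 12 weeks and continuing on placebo throughout are different experiences, and the average over both belongs to neither. The sponsor evidently regards earlier treatment as important, because the 2 mg patients are split by it in the tables and the placebo patients in the listings. The placebo tables are the exception.

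The primary objective is long-term safety, so most is at stake there. The Placebo column is the only one without etrasimod in the extension, and a reader will look to it for a background rate of adverse events, laboratory changes and vital-sign changes. If part of the column was on etrasimod until the extension began, it does not provide that background.

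**Working it through.** The plan states no sample size, rate or count that could be reproduced here. The check therefore reads the SAP rules side by side and adds simple arithmetic on the visit schedule and on assumed rates.

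**1. Who is in each column** (SAP sections 1, 4 and 12)

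| Patients | Week 12 status | APD334-003 drug | Extension drug | Summary column |
|---|---|---|---|---|
| Amendment 02, randomised | responder | etrasimod | 2 mg | 2 mg |
| Amendment 02, randomised | responder | etrasimod | placebo | Placebo |
| Amendment 02, not randomised | responder | placebo | placebo | Placebo |
| Amendment 02, open-label | non-responder | any | 2 mg | 2 mg |
| Amendment 03 | responders only (section 1); completers (section 12) | any | 2 mg | 2 mg |
| Amendment 04 | any completer | any | 2 mg | 2 mg |

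Placebo thus holds two populations, both made up of Week 12 responders. The two accounts of Amendment 03 entry disagree and need reconciling.

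**2. What the safety rules do to the Placebo column**

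- *Adverse events (SAP 9.1).* An event that began in APD334-003 and continues into, or ends in, the extension counts as treatment-emergent. For a withdrawn patient, an event that started on etrasimod is tabulated under Placebo. For a never-treated patient, the same rule brings in only events that started on placebo.
- *Laboratory values and vital signs (SAP 9.2, 9.3).* Changes are shown from two baselines. The APD334-003 baseline precedes study drug in both sources. The APD334-005 baseline is Day 1 before dosing; it follows etrasimod in withdrawn patients only, so their change may include recovery from a drug effect. Blood counts are the obvious case: Protocol 5.5.2 keeps white-cell and lymphocyte counts blinded because the drug's mechanism could reveal treatment.
- *Overall exposure (SAP 7.2.2).* Days on any study drug are added over both studies.

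**3. Exposure arithmetic.** APD334-003 lasted 12 weeks (Protocol Synopsis), and Amendment 02 patients had their final assessment at Week 52 (SAP 3.1). For full dosing:

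- induction: 12 × 7 = 84 days
- extension: (52 − 12) × 7 = 280 days
- overall: 84 + 280 = 364 days

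These match the top exposure categories in SAP 7.2.2 (280 days for the extension, 364 days overall). Every placebo completer shows 364 days. If a share *w* of them was withdrawn from etrasimod, mean etrasimod exposure in the column is 84*w*: 16.8 days at *w* = 0.2 and 67.2 days at *w* = 0.8. The table shows 364 in either case.

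**4. Response in a mixed column (assumed rates).** Column rate = *w* × 0.40 + (1 − *w*) × 0.60, with 40% in withdrawn and 60% in never-treated patients.

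| *w* | 0.2 | 0.4 | 0.6 | 0.8 |
|---|---|---|---|---|
| Column rate | 0.56 | 0.52 | 0.48 | 0.44 |

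If both sources have the same rate (0.50 and 0.50), the column reads 0.50 at every mix. The mixing matters only as far as the sources differ, which the documents do not tell us.

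**5. Does SAP 8.3 already repair the response tables?** It puts three proportions in one presentation: Week 12, end of treatment, and both. Response among Week 12 responders is then *both* ÷ *Week 12*. As a test, assume no drug effect, with end-of-treatment response of 70% in Week 12 responders and 35% in non-responders, and a responder share *r* in the 2 mg column.

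| Column | Week 12 | Both | End of treatment | Both ÷ Week 12 |
|---|---|---|---|---|
| 2 mg, *r* = 0.4 | 0.40 | 0.28 | 0.28 + 0.21 = 0.49 | 0.70 |
| 2 mg, *r* = 0.7 | 0.70 | 0.49 | 0.49 + 0.105 = 0.595 | 0.70 |
| Placebo | 1.00 | 0.70 | 0.70 | 0.70 |

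The end-of-treatment row alone differs by 21 or 10.5 points, but the ratio agrees across columns. The like-for-like figure can therefore be recovered. It is not printed, and it has no confidence interval, because the default denominator in SAP 4 is the whole group. It also does nothing to separate the two placebo sources.

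**The case against.** The other side has a good case. No between-group comparison is planned in either document, so no test is made invalid. The Placebo group is left over from a superseded design, and the SAP discloses this in several places. The study is about etrasimod, and the 2 mg patients are already tabulated by earlier treatment. The section 8.3 rows let a careful reader adjust for Week 12 status, and each placebo patient's APD334-003 treatment is in the listings. Splitting a remnant group will also leave small cells.

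Most of this stands for efficacy: after section 8.3, what remains there is convenience and a missing interval. Two qualifications apply. The Week 12 row uses the SAP's response definition, which section 12 says was updated; the documents do not show that it matches the one used to assign treatment, so the Placebo entry may not be exactly 100%. And the division gives no split by earlier treatment within Placebo.

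For safety the objection is weaker. No readable safety table separates the two sources, and rebuilding incidences or mean changes from listings is not something a report reader can be expected to do.

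Part of the subgroup text in the SAP is blacked out, and figures are missing next to the layout table. Some of what is asked for here may already be planned.

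**Conclusion.** The point holds as a matter of presentation, and it is a cheap improvement. As the readable SAP stands, the Placebo column describes neither patients withdrawn from etrasimod nor patients on placebo throughout, and the adverse-event, exposure and baseline rules carry earlier etrasimod into it for one source only. This rests on the assignment rules in SAP 12 and the layout in SAP 4, and on no redacted passage providing the split.

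A reader might go further and infer that the tables are biased against etrasimod, by 10 to 21 points on response, because an all-responder column stands beside one that includes non-responders. The documents do not support that.

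- There is no planned contrast to be biased.
- The direction is not settled. Under Amendment 02 responders stayed blinded, whereas non-responders and later entrants took 2 mg open-label. Stool frequency and rectal bleeding are patient-reported, so open-label reporting could favour 2 mg. Every placebo patient was due for final assessment at Week 52, while Amendment 03 and 04 patients were assessed at Week 46, which allowed longer for response to be lost on placebo.
- The 10 to 21 points come entirely from the assumed 70% and 35%, and the section 8.3 rows would expose that gap.

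Column sizes and rates are not given, so no size or direction is claimed.

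**What to change.** 1. In the SAP section 4 layout and in section 12, split Placebo into two columns, *etrasimod in APD334-003, then placebo* and *placebo in both studies*, and keep the total. This is essential for the adverse-event, exposure, laboratory and vital-sign tables.
2. In the section 8.3 presentation, add for response and for remission a row giving the end-of-treatment proportion among Week 12 responders in each column, with its own denominator and the SAP's 90% confidence interval.
3. Footnote the efficacy tables: Placebo patients were all assigned as Week 12 responders under Amendment 02, with final assessment at Week 52; the 2 mg column includes non-responders and patients finally assessed at Week 46.
4. Reconcile the Amendment 03 entry rule between SAP sections 1 and 12, so that the footnote is correct.

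The cost is SAP wording and table shells. The listings already use earlier treatment, and section 8.3 already uses Week 12 response, so no new data are needed. The downside is one more column with small numbers, to be read as description only. If a redacted subgroup section already has part of this, a cross-reference will do for that part.
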